4.10. Premature Discontinuation of the Trial

IPM has the right to terminate this trial at any time for any reason. If the trial is prematurely terminated, the investigator must promptly inform the participants and the IRBs/IECs, and ensure proper medical follow-up of participants in consultation with IPM. If the trial is prematurely terminated, all procedures and requirements pertaining to the archiving of the trial documents will be observed. IPM will provide the research centres with instructions on the proper disposition of any clinical supplies at the centre.

5. Trial Procedure Details

5.1. Informed Consent

The informed consent documents will include all the information about the trial required by GCP and will make provision for the dated signatures of the participant, the principal investigator or designated trial staff conducting the informed consent process, and when required, also for a dated signature by an impartial witness. The informed consent process will be administered at the Screening Visit.

The informed consent process will include adequate time for each potential participant to

have any trial related questions answered by appropriately qualified and trained trial staff as designated by the investigator, and the entire process will be documented in the source documents.

At screening, potential participants who agree to participate in the trial will sign and date the ICF. The ICF will also be signed and dated by the trial staff administering the consent process as delegated by the principal investigator according to the research centre SOP. If a potential participant is functionally illiterate, the informed consent document(s) and any written study-related materials must be read to her in the language best understood by the potential participant in the presence of an impartial literate witness. After the illiterate participant has orally consented to participate in the trial, and, if capable of doing so, has signed the ICF or provided a thumbprint or mark that was witnessed by the impartial witness, this impartial witness must sign and personally date the ICF. By signing the ICF the impartial witness attests that the information in the participant information sheet and any other written information was explained to, and apparently understood by, the participant or the participant's legally acceptable representative and that informed consent was freely given by the participant or the participant's legally acceptable representative.

The signed and dated ICFs will be retained at the research centre. A copy of the signed and dated ICFs will be offered to the participant. If the participant is not willing to receive the documents, the second copy will be retained at the research centre. Likewise, during the trial, signed and dated ICF updates and any amendments to written trial-related materials to be given to participants will be offered to the participant but retained at the research centre if the participant is unwilling to receive the documents. Documentation of the participant's refusal to accept a copy of the ICF(s) or other trial-related materials will be noted in the source documents.

The consent documents and any trial-related materials given to the participant will be translated and back-translated in the local languages according to local IRB/IEC requirements and regulatory authority guidelines. Information in the informed consent documents and trial-related material will be verbally communicated by trial staff, in the language preferred by the participant, and copies of the documents and trial-related materials will be offered to her in her preferred language. Documentation will be required to verify who performed translation/back-translation of the materials as well as a written statement by the translator indicating that the consent form(s) is an accurate translation of the accompanying English version. This is the principal investigator's responsibility.

All research centre-specific informed consent documents will first be reviewed and approved by IPM and then approved by the responsible IRB and/or local IEC prior to administration to the participants.

If new information becomes available which may be relevant to the participant's willingness to continue trial participation, the information will be provided *via* IRB and/or IEC-approved revised informed consent documents or addenda to the original informed consent documents in a timely manner and will be signed and dated by the participant in the same manner described above.

5.2. Comprehension Assessment Checklist

Trial staff will assess the potential participant's understanding of informed consent information prior to obtaining a signature on the ICF at the Screening Visit. This assessment will be done using a standardised comprehension assessment checklist. All comprehension problems that are discovered during the assessment will be discussed until staff member(s) are satisfied that the participant can verbalise her understanding of the issue. This process will be documented on the comprehension assessment checklist. This checklist will be recorded in source documentation at the research centre. A participant who cannot demonstrate comprehension of the informed consent information will not be enrolled in the trial.

5.3. HIV Counselling

5.3.1. *HIV Pre-and post-Test Counselling*

At all visits where HIV testing is performed, pre- and post-test counselling will be provided according to the National Guidelines for HIV Counselling and Testing. Adaptations of these guidelines in accordance with locally accepted standards of practice are allowed. Each research centre will document the counselling policies and procedures prior to trial implementation for purposes of staff training, quality assurance, and trial monitoring.

A comprehensive package of post-test counselling and psychosocial support will be provided to women who test HIV reactive at any point during trial participation. Initial counselling services will be provided at the research centre and women will be referred for additional counselling, support services and treatment. These services will be identified by the research centres prior to trial initiation and referral procedures will be documented in writing by the centre.

5.3.2. *HIV/STI Risk Reduction Counselling*

HIV/STI risk reduction counselling will be in accordance with local guidelines. Counselling will be provided at all research centre visits. Efforts will be made to ensure standardisation of risk reduction counselling at the trial research centres.

NOTE: Risk reduction counselling will include recommendation of male condom use. Participants will be provided with a supply of male non-spermicidal condoms during each trial visit, if they are willing to accept them. The use of female condoms is permitted in this trial.

5.4. HIV Testing and Management

The research centres will inform IPM Medical Safety of any new HIV seroconversions within 48 hours of diagnosis. The applicable regulatory authorities and independent ethics committees who require expedited notification of HIV seroconversion will be notified by either IPM or the research centre in accordance with standard operating procedures and policies of the regulatory authorities or independent ethics committees. The details of the HIV rapid test kits will be specified in the Laboratory Manual, as part of the SOM. Participants will be tested for HIV using two highly sensitive antibody rapid tests (Test 1 and Test 2).

5.4.1. *Screening Visit*

If both test results are non-reactive, the participant could potentially be enrolled in the trial if she is otherwise eligible.

If both Test 1 and Test 2 are reactive at screening, the potential participant is considered to be HIV seropositive and not eligible for enrolment. Initial counselling services will be provided at the research centre and the participant will be referred for additional counselling, support services and treatment. These referral systems will be implemented by research centres prior to trial start. It is the participant's responsibility to follow up with relevant medical services once referral has been initiated by the research centre.

If Test 1 and Test 2 yield discordant results, a highly specific HIV antibody Test 3 will be performed. If Test 3 is reactive then the potential participant is considered to be HIV-seropositive and is not eligible for enrolment. If Test 3 is non-reactive, the person is considered to be potentially HIV-seronegative and can be given a date for enrolment into the trial. Refer to Appendix B: HIV Testing Algorithms.

A blood sample will be obtained by venepuncture to be sent for sample storage locally or at a central laboratory, for potential HIV-1 RNA PCR and viral genotype resistance testing if the participant seroconverts (blood volume specified in Appendix C). Storage samples for participants who do not enrol will be destroyed according to research centre SOPs.

NOTE: For the purposes of HIV rapid testing at screening, blood may be obtained by finger prick or venous sampling. If the national regulatory authority of the country in which the research centre is situated requires that a national testing algorithm be used during the screening process, this will be performed, in addition to the IPM 032 HIV testing algorithm, as part of the screening process and documented as such.

5.4.2. *Enrolment Visit*

On the scheduled day of possible enrolment, the participant will be tested for HIV and will only be enrolled if the results are considered to be HIV-seronegative and the participant is otherwise eligible.

Test 1 and Test 2 will be performed. If both test results are non-reactive and there is no history to suggest recent exposure that could be masked during the window period, the potential participant will be considered HIV-seronegative and eligible for enrolment. A blood sample will be obtained by venepuncture to be sent for sample storage locally or at a central laboratory, for potential HIV-1 RNA PCR and viral genotype resistance testing if the participant seroconverts (blood volume specified in Appendix C). Storage samples for participants who do not enrol will be destroyed according to local SOPs.

If both Test 1 and Test 2 are reactive, the participant is considered to be HIV seropositive and not eligible for enrolment. Initial counselling services will be provided at the research centre and the woman will be referred for additional counselling, support services and treatment.

A rapid Test 3 will be performed for all discordant rapid test results. If Test 3 is reactive then the potential participant is considered to be HIV-seropositive and not eligible for

enrolment. If Test 3 is non-reactive, the participant is considered to most likely be HIV-seronegative, and a sample will be collected for HIV-1 RNA PCR testing and the Enrolment Visit should be re-scheduled within the screening window period (split visit). If the HIV-1 RNA PCR does not detect HIV RNA copies, the participant can be enrolled. Storage samples should be collected on the second day of the split visit. If the HIV-1 RNA PCR does detect HIV RNA copies then she is not eligible for enrolment. She will be counselled and referred to the local health facilities for appropriate follow-up. Refer to Appendix B: HIV Testing Algorithms.

5.4.3. *Trial Visits and LPUV*

The rapid and confirmatory laboratory tests used in the HIV-testing algorithm will detect both subtypes, HIV-1 and HIV-2. The testing algorithm (refer to Appendix B) will be applied for all Trial Visits and LPUV. HIV testing while the participant is enrolled in the trial will be performed on blood samples obtained by venepuncture (blood volumes specified in Appendix C).

If both the HIV rapid tests (Test 1 and Test 2) are non-reactive, the participant will be considered HIV-seronegative and continue using the IP. If both HIV rapid tests are reactive, IP will be withheld until HIV infection has been confirmed. Trial procedures relevant to the LPUV will be performed. Additional confirmatory testing will be performed by Western Blot and other confirmatory tests, where appropriate. IP may be re-introduced after consultation with IPM, if confirmatory test(s) indicate(s) that the participant is not HIV infected. The participant must have a negative pregnancy test prior to re-introduction of IP. A pelvic examination should be performed according investigator's discretion prior to re-introduction of IP if clinical indicated. If confirmatory test(s) indicate(s) that the participant is HIV infected, the participant will be permanently discontinued from IP and the trial.

If the Test 1 and Test 2 results are discordant, a HIV rapid Test 3 will be performed on the same blood sample as used for Test 1 and Test 2. If Test 3 is reactive, IP will be withheld until HIV infection has been confirmed. Trial procedures relevant to the LPUV will be performed. Additional confirmatory testing will be performed by Western Blot and other confirmatory tests, where appropriate. IP may be re-introduced after consultation with IPM, if confirmatory test(s) indicate(s) that the participant is not HIV infected. The participant must have a negative pregnancy test result prior to re-introduction of IP. A pelvic examination should be performed according investigator's discretion prior to re-introduction of IP, if clinical indicated. Nucleic acid-amplification testing (NAAT) by a HIV-1 RNA PCR test will be performed on stored samples in reverse sequential order to estimate the time point of HIV infection. The participant will be counselled and referred for appropriate counselling and care.

If Test 3 is non-reactive, the participant is considered to be HIV-seronegative. The participants who have discordant HIV test results at Trial Visits will continue on IP and be requested to return for repeat HIV rapid testing after two weeks. In such cases the research centre will notify the IPM Clinical Project Manager or designee. Additional confirmatory tests may be indicated at any stage in consultation with the IPM Clinical Project Manager or designee. If a similar result is obtained on testing after two weeks, a sample should be collected for a quantitative HIV-1 PCR test and the research centre will notify the IPM Clinical Project Manager and Laboratory Specialist.

If the HIV-1 RNA PCR result is undetectable:

- The participant is considered to not be HIV-infected.
- The participant should continue in the trial with HIV rapid testing only performed at scheduled visits, even if the same pattern of discordant results continues. It will not be necessary to recall the participant for 2-weekly testing.
- The research centre will notify the IPM Clinical Project Manager or designee of the outcome.

If the HIV-1 RNA PCR result is detectable:

- The participant should be considered HIV-infected and IP should be discontinued immediately. The research centre will notify the IPM Clinical Project Manager or designee immediately.

All enrolled participants will in addition, have blood samples collected at each trial visit to be stored locally or at a central laboratory, for possible viral genotype resistance testing and HIV-1 RNA PCR testing. If a participant subsequently seroconverts (i.e. is confirmed HIV-positive) while on the IP, the stored samples will be tested in reverse sequential order until an undetectable PCR test result is obtained. This will be conducted to approximate the period of HIV infection. If the enrolment HIV-1 RNA PCR test result is positive, the participant is not considered to have been infected while using the IP.

Blood (blood volume as specified in Appendix C) and vaginal fluid samples will also be obtained for dapivirine measurement at the point of HIV seroconversion according to the HIV testing algorithm described above. Stored samples (blood and vaginal fluids) will be analysed retrospectively as described in Section 5.17.

Any participant who is confirmed HIV-infected while on the trial will be permanently discontinued from IP and the trial. An exit visit will be scheduled approximately 1-2 months following IP discontinuation. Initial counselling services will be provided at the research centre and women will be referred for additional counselling, support services and treatment. In addition, these women will be offered the option of enrolling for IPM's seroconverter protocol.

In an instance where a participant is determined to be HIV-seropositive (as determined by HIV rapid tests, Western Blot; and any other confirmatory tests, if applicable), but cannot be confirmed as HIV-infected (HIV RNA PCR) the participant will be discontinued from IP and the protocol-required procedures as per original trial visit schedule will be conducted at the investigator's discretion. Samples for measurement of dapivirine levels will no longer be collected. Additional testing to demonstrate HIV infection may be performed. Participants will be followed up until the exit visit according to the original enrolment date.

5.4.4. ***Exit Visit***

For participants confirmed as HIV-negative prior to the exit visit

If both HIV rapid tests (Test 1 and Test 2) are non-reactive, the participant will be considered HIV-seronegative. If both Test 1 and Test 2 are reactive, additional confirmatory testing will be performed by Western Blot and other confirmatory tests, where appropriate. Samples for possible viral genotype resistance testing and HIV-1

RNA PCR testing will be collected. Once HIV infection has been confirmed, this will be considered an HIV seroconversion after product discontinuation and may be a combination of both women infected during IP use who seroconverted after IP discontinuation, as well as women infected after IP use. Nucleic acid-amplification testing (NAAT) by a HIV-1 RNA PCR test will be performed on stored samples in reverse sequential order to estimate the time point of HIV infection.

Initial counselling services will be provided at the research centre and women will be referred for additional counselling, support services and treatment.

A HIV rapid Test 3 will be performed for discordant rapid Test 1 and Test 2 results. If Test 3 is reactive then the participant will be considered to be HIV-seropositive. Additional confirmatory testing will be performed by Western Blot and other confirmatory tests, where appropriate. Samples for possible viral genotype resistance testing and HIV-1 RNA PCR testing will be collected. The participant will be counselled and referred to local health facilities for social support or other medical services as clinically indicated. If Test 3 is non-reactive, the participant is considered to be HIV-seronegative and will be counselled appropriately. Refer to Appendix B: HIV Testing Algorithms, and Appendix C: Visit Schedule and Blood Volumes.

For participants confirmed as HIV-infected prior to the exit visit

As stated in Section 5.4.3 above, an exit visit will be scheduled approximately 1-2 months following confirmed HIV-seroconversion and IP discontinuation. Blood samples for viral genotype resistance testing and HIV-1 RNA PCR will be collected from these participants, but no further HIV counselling and testing will be done unless indicated for additional confirmatory testing.

Participants who become infected with HIV during the course of an IPM trial will be referred for appropriate HIV-related care and ARV therapy as above. The threshold for initiation of ARV treatment will be determined with reference to the WHO treatment guidelines if no country specific guidelines are available. Women who become pregnant and HIV positive during the trial will be referred for appropriate Prevention of Mother-to-Child Transmission (PMTCT) services.

The research centres will inform IPM Medical Safety of any new HIV infections within 48 hours of diagnosis. The applicable regulatory authorities and ethics committees who require expedited notification of HIV seroconversion will be notified by either IPM or the research centre in accordance with standard operating procedures and policies of the regulatory authorities or ethics committees.

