Participants will receive pre- and post-test counselling for HIV and undergo HIV testing. HIV/STI risk reduction counselling (including provision of male condoms, should they wish to receive them) and contraceptive counselling will also be provided at the exit visit. Contraception and STI treatment will be provided or the participant will be referred, if needed. The following procedures are not required, but may be conducted if clinically indicated: physical and pelvic examination, cervicovaginal sample collection for STI testing, provision of treatment and/or referral for STIs and other findings, laboratory testing for safety assessments, urine dipstick analysis (microscopy only if clinically indicated) and cervical sample collection for cytology (if no result is evident within the previous year, or abnormal at last cervical cytology).

Blood samples will be collected for storage, and will be tested retrospectively by HIV-1 RNA PCR and HIV viral genotype resistance testing subsequent to confirmed HIV seroconversion.

Participants will then be considered to have completed trial participation.

STATISTICAL CONSIDERATIONS:

Sample Size:

This is an open-label, follow-on trial to IPM 027 to evaluate the safety of and adherence to Dapivirine Vaginal Ring-004, inserted at monthly intervals in healthy, HIV-negative women who have participated in the IPM 027 trial. No formal sample size or power calculations have thus been performed.

It is expected that approximately 70% of the participants enrolled in IPM 027 will participate in this trial. Therefore, a total sample size of approximately 1400 HIV-negative women is anticipated.

Statistical Analyses:

The primary analysis will focus on safety as well as adherence assessments, performed under the intent-to-treat (ITT) principle. As it is possible that the inclusion of non-adherent participants or participants who discontinued from ring use may artificially lower the rates of safety outcomes, additional analyses will be conducted on the per-protocol population, which will include only participants who were adherent to the protocol.

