3.2. Trial Duration

Each participant will engage in the screening process for up to 45 days prior to enrolment and will use the Dapivirine Vaginal Ring-004 for a period of up to 12 months. IPM will have the option to extend this trial period. Accrual will take place over approximately 6 months and those participants who are enrolled more than 6 months after the onset of the study site's accrual period may have a shortened follow-up period.

Each participant will have an exit visit 1-2 months after ring discontinuation, to assess safety and identify HIV seroconversions after product discontinuation.

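### At the Exit visit, discordant rapid tests with a non-reactive Test 3 are settled as HIV-negative without a repeat test or PCR, and no later visit can correct the call

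*Protocol*

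**What the plan says.** The result in question is the same throughout: Test 1 and Test 2 discordant, Test 3 non-reactive.

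- **Screening (Protocol 5.4.1):** "the person is considered to be potentially HIV-seronegative and can be given a date for enrolment into the trial". The Enrolment visit then includes an HIV test for every woman.
- **Enrolment (5.4.2):** she is "considered to most likely be HIV-seronegative, and a sample will be collected for HIV-1 RNA PCR testing". The visit is split, and she is enrolled only if no RNA is detected.
- **Trial Visits (5.4.3):** she is called seronegative and stays on the ring, but will "be requested to return for repeat HIV rapid testing after two weeks". The next step is also fixed: "If a similar result is obtained on testing after two weeks, a sample should be collected for a quantitative HIV-1 PCR test".
- **Exit (5.4.4):** "If Test 3 is non-reactive, the participant is considered to be HIV-seronegative and will be counselled appropriately". Nothing further is required in the prose.

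Protocol 3.2 gives the purpose of the Exit visit as "to assess safety and identify HIV seroconversions after product discontinuation". The Synopsis closes its description of that visit with "Participants will then be considered to have completed trial participation", and item (j) of 4.5 likewise exits her from the trial. Item (g) of 4.5 collects blood at Exit for possible RNA PCR. Under 5.17 and note (c) of Appendix A, stored blood is tested once seroconversion is confirmed; 5.17 adds testing of a random sample of HIV-negative women.

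**The concern.** Discordant rapid tests can be an early sign of seroconversion. Elsewhere the protocol does not leave this result as the last word: either a specific follow-up step is triggered or another scheduled test is still to come. Exit has neither, although finding late seroconversions is one of its stated purposes.

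Two things are at stake. The first is the woman's diagnosis: she would be counselled as negative and discharged although one of her rapid tests was reactive. The second is endpoint classification. SAP 9.3.1 starts the reverse-sequential PCR look-back only when HIV-1 is detected at Exit. If she is called negative, the look-back never starts, so nobody learns whether she was already RNA-positive at the LPUV. Section 5.4.4 itself recognises that seroconversions found at Exit may include women infected during ring use.

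**Working it through.** The protocol states no figure to reproduce, so the first check is a comparison of what follows the same result at each visit.

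| Visit | Step triggered by the discordance | Later scheduled HIV test |
|---|---|---|
| Screening (5.4.1) | None | Yes, at Enrolment |
| Enrolment (5.4.2) | RNA PCR before entry | Yes, Trial Visits |
| Trial Visits (5.4.3) | Two-week repeat, then PCR if similar | Yes |
| LPUV (5.4.3) | Unclear | Yes, at Exit |
| Exit (5.4.4) | None in the prose | None |

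The LPUV entry is marked unclear because 5.4.3 applies its algorithm to Trial Visits and the LPUV, while the recall sentence names Trial Visits and describes women who continue on product. It does not matter here, because the Exit test follows for a woman on the scheduled course (4.9 makes Exit optional after early discontinuation). Exit is the only row with neither a triggered step nor a later test.

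Effect of one missed case on the analyses in SAP 9.3.1:

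- **Analysis 3** counts every confirmed seroconverter infected after enrolment, so it loses the case.
- **Analyses 1 and 4** lose it only if she was already RNA-positive at or before the LPUV.
- **Analysis 2** loses it only if infection on product could not have been ruled out.

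Size for Analysis 3. The documents give neither the accrued woman-years nor the rate, so I assume 1400 woman-years (about 1400 women for up to 12 months) or 1000, and a true rate of 1 to 3 per 100 woman-years.

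- Change per missed case = 100/PY. At 1400: 100/1400 = 0.071 per 100 woman-years. At 1000: 100/1000 = 0.100.
- Half-width of the 95% CI, from the footnote to Table 14.3.7.7, is 1.96 × √([n/PY]/PY) × 100 = 1.96 × √n/PY × 100.

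| Assumed PY | Rate per 100 | n | Half-width | One case as share of half-width |
|---|---|---|---|---|
| 1400 | 1 | 14 | 0.524 | 0.071/0.524 = 13.6% |
| 1400 | 3 | 42 | 0.907 | 0.071/0.907 = 7.9% |
| 1000 | 1 | 10 | 0.620 | 0.100/0.620 = 16.1% |
| 1000 | 3 | 30 | 1.074 | 0.100/1.074 = 9.3% |

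The number of such cases cannot be estimated. The documents give no discordance rate at Exit and no fraction of discordant results that are true infections.

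**The case against.** The strongest objection is that the governing rule may be elsewhere. Section 5.4.4 refers to Appendix B, and SAP 9.3.1 says seroconversion is determined by the Appendix B algorithm. Figure 5, the Exit algorithm, is not shown and may contain a repeat or PCR step. This stands as a reason to check the figure first. It does not cancel the prose, which gives a complete instruction that a site could follow as written.

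The second objection is that a lighter rule at Exit is reasonable, because the stricter steps protect a decision to start or continue the ring and at Exit there is no such decision. That explains why urgency is lower. It does not remove the need for a correct diagnosis at a visit meant to find seroconversions, and the protocol gives no such rationale.

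Third, other routes exist. Section 5.4.3 says "Additional confirmatory tests may be indicated at any stage in consultation with the IPM Clinical Project Manager or designee"; 4.6 allows unscheduled HIV testing; SAP 9.3.1 describes ad hoc HSMC advice on inconclusive results; SAP 10.6.1 allows PCR where there is reason to suspect infection; 5.3.1 may bring counselling and referral. All of this stands, but each route is discretionary, depends on chance (the random sample in 5.17), or requires no further HIV test.

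A reader might infer that every earlier visit has a test triggered by the discordance and that Exit alone lacks one. The documents do not support that: the test after Screening is routine, and the recall rule does not clearly fit the LPUV. A reader might also take the note in SAP Table 10, that RNA PCR is done only for seroconverters, as barring PCR for this woman. It is a data-source remark in a variable table, and read as a rule it would contradict the PCR step in 5.4.3.

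**Conclusion.** The point holds as a gap in the prose rule for Exit. This is the last HIV test in the trial, and a result that would need PCR at Enrolment, or a repeat and possibly PCR at a Trial Visit, is closed as negative with no required confirmation. This is conditional on Figure 5 not already supplying the step.

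The numerical consequence is small and may be zero. Under the assumed woman-years and rates, one missed case is about 8% to 16% of the CI half-width for Analysis 3, and Analyses 1, 2 and 4 are affected only under the conditions set out above. A reader might infer that the reported incidence is materially biased downward. The documents do not support that: they give no count of such women, the HIV rate is a descriptive secondary endpoint, and one case would not change a conclusion. The case for acting rests on the individual woman's diagnosis and a correct Exit classification, at little cost.

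**What to change.** First confirm what Figure 5 requires for discordant Tests 1 and 2 with a non-reactive Test 3 at Exit. If it already mandates a repeat or PCR, bring the 5.4.4 prose into line with it.

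Otherwise, state in 5.4.4 (with Figure 5 to match) and in SAP 9.3.1 that any woman with this result at Exit has HIV-1 RNA PCR on the Exit storage sample from 4.5(g) before her HIV outcome is finalised. If RNA is detected, run the reverse-sequential look-back so that the infection is dated and assigned to the right analyses. If no usable sample exists, recall her for testing. The PCR has to be done before residual specimens are destroyed under 5.17.

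The cost is a few PCR assays on blood already scheduled for collection, about one sentence in each document, and a short delay in closing out those women. The note to 4.5 already accepts a late Exit visit while confirmatory results are pending, so some delay for this reason fits the existing plan.
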